8.1.3.2 Short Form 12 Health Survey (SF-12)

The Standard SF-12 ([Appendix 4](#)) captures the subject's views about their own functional health and well-being in the past 4 weeks in 12 items. There are eight health domains measured using the SF-12 as follows:

- General Health (GH) – question 1 with a range of 1-5
- Physical Functioning (PF) – questions 2 and 3 with a range of 1-3 each
- Role-Physical (RP) – questions 4 and 5 with a range of 1-2 each
- Role-Emotional (RE) – questions 6 and 7 with a range of 1-2 each
- Bodily Pain (BP) – question 8 with a range of 1-5
- Mental Health (MH) – questions 9 and 11 with a range of 1-6 each
- Vitality (VT) – question 10 with a range of 1-6
- Social Functioning (SF) – question 12 with a range of 1-5

The SF-12 responses will be scored using OPTUM® PRO CoRE software, version 1.4 or higher, producing scores for the 8 health domains and the physical component summary (PCS) and mental component summary (MCS). Higher scores reflect higher functioning and well-being. The SF-6D index, a health state classification measure scored from 0.0 (worst health state) to 1.0 (best health state), will be derived based on the SF-12.

8.1.3.3 The Expanded Prostate Cancer Index Composite for Clinical Practice (EPIC-CP)

The EPIC-CP ([Appendix 5](#)) asks questions about the subject's health and symptoms in the last four weeks. There is one overall urinary function question with possible responses of No Problem, Very small problem, Small problem, Moderate problem, and Big problem. Additionally, there are 5 domains with 3 questions each and possible integer score responses ranging from 0 to 4 as follows:

- Urinary Incontinence Symptom Score – questions 2-4
- Urinary Irritation/Obstructive Symptom Score – questions 5a-5c
- Bowel Symptom Score – questions 6a-6c
- Sexual Symptom Score – questions 7-9
- Vitality/Hormonal Symptom Score – questions 10a-10c

The total score for each domain is the sum of the individual scores within the domain, i.e., the total scores in each domain range from 0 to 12 and higher scores reflect worse symptoms. The pooled scores from all domains, the sum of all domain total scores, range from 0 to 60 and capture the Overall Prostate Cancer Quality of Life Score. Scores will be set to missing if any of the individual scores are missing.

8.1.3.4 International Prostate Symptom Score (I-PSS)

The I-PSS ([Appendix 6](#)) consists of 7 questions about urinary symptoms (scores range from 0 to 5 each) and one question about quality of life (score ranges from 0 to 6), with higher scores indicating worse symptoms. The total I-PSS score is the sum of the scores from questions 1 to 7 and ranges from 0 to 35. Scores will be set to missing if any of the individual scores are missing.

8.2 Leukapheresis Variables

Number of Leukapheresis Received

Count of leukapheresis received is captured on the Leukapheresis Form at the scheduled 3 visits and unscheduled visits.

Central Venous Catheter (CVC) use

CVC use is defined as occurrence captured on the Central Venous Catheter Summary Form at any visit.

8.3 Study Drug (Sipuleucel-T) Exposure Variables**Dose Interruption**

A dose interruption is defined as any interruption during the administration (infusion) of sipuleucel-T. Dose interruptions are recorded on the Sipuleucel-T - IV/Infusion Administration CRF page and indicated as a Yes response to “Was the infusion interrupted?”.

Dose Volume Infused

Actual dose volume administered is defined as the actual amount infused and is collected in the “Volume infused” field in mL.

Number of Infusions Received

Count of infusions received captured on the Infusion Summary CRF in the End of Active Phase folder.

Reasons for Less Than 3 Infusions

Reasons for receiving less than the 3 infusions planned are captured on the Infusion Summary CRF in the End of Active Phase folder.

8.4 Safety Endpoints and Variables**8.4.1 Adverse Events (AEs)**

An AE is defined as any untoward medical occurrence in a subject while participating in a study that does not necessarily have a causal relationship with sipuleucel-T. An AE can, therefore, be any unfavorable and unintended sign (e.g., abnormal laboratory finding), symptom, or disease temporally associated with sipuleucel-T, whether or not considered related to sipuleucel-T. AEs include exacerbation of a pre-existing illness, an increase in frequency or intensity of a pre-existing episodic event or condition, a condition detected or diagnosed after product administration (even though it may have been present prior to the start of the study) or a continuous persistent disease or symptoms present at Screening that worsens following the start of the study.

All AEs (and SAEs) in the sipuleucel-T arm and control arm will be collected from randomization through the subject’s last study visit. For this study, treatment emergent adverse event (TEAE) is not defined. All adverse events occurring after the first leukapheresis (after randomization for the control arm) will be summarized.

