6.7 Restricted Therapies During Sipuleucel-T Treatment Period

Certain therapies and procedures could confound the results of this study. Therefore, subjects who are randomized to the sipuleucel-T arm and receive any of the following, 30 days prior to the first infusion until 30 days after the last infusion, will discontinue sipuleucel-T treatment (Section 6.3.1):

- Any immunosuppressive therapy, including systemic steroids. Use of inhaled, intra-nasal, intra-articular, and topical steroids is allowed. Oral or IV steroids to prevent or treat IV contrast reactions are allowed
- Blood products
- GM-CSF or G-CSF
- Any vaccinations

Subjects that discontinue sipuleucel-T treatment and have received > 0 mL of sipuleucel-T will remain in the Active Phase and follow the schedule of events (Table 1).

6.8 Restricted Therapies from Randomization to End of Active Phase (Sipuleucel-T and Control Arms)

Certain therapies and procedures could confound the results of this study. Therefore, subjects who receive any of the following will go from Active Phase of the study to the Follow-up Phase of the study:

- Any local or systemic therapy or procedures for prostate cancer (e.g., ADT, radical prostatectomy, external beam radiation or brachytherapy)
- Any local or systemic therapy or procedure targeting the prostate (e.g., transurethral resection of the prostate (TURP) or 5-alpha reductase inhibitor)
- Major surgery at the discretion of the sponsor's Medical Monitor
- Any investigational product for prostate cancer or other condition (per sponsor's Medical Monitor approval)
- Any other therapy at the discretion of the sponsor's Medical Monitor

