9.1.4 Recording and Reporting Adverse Events

All AEs and SAEs in the sipuleucel-T arm and control arm will be collected from randomization through the subject’s last study visit. AEs and SAEs will be reported and recorded in the subject’s medical record and entered on their eCRF.

All AEs and SAEs reported in either the sipuleucel-T or control arms will be followed by the investigator until resolution, return to baseline, or the investigator determines that no further improvement is expected until study completion. The start and stop dates, description, seriousness, toxicity, relationship to study treatment, and outcome will be recorded.

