9.2 Serious Adverse Events

9.2.1 Definition of Serious Adverse Event

An SAE is defined as any adverse drug experience occurring at any dose that results in any of the following outcomes: death, a life-threatening adverse drug experience, subject hospitalization or prolongation of an existing hospitalization, a persistent or significant disability/incapacity, or a congenital anomaly/birth defect. An important medical event that may not result in death, be life-threatening, or require hospitalization may be considered an SAE when, based upon appropriate medical judgment, it may jeopardize the subject and may require medical or surgical intervention to prevent one of the outcomes listed in this definition. Examples of such medical events include allergic bronchospasm requiring intensive treatment in an emergency room or at home, blood dyscrasias or convulsions that do not result in subject hospitalization, or the development of drug dependency or drug abuse.

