- PROs/Quality of life questionnaires (Max-PC, SF-12, EPIC-CP, and IPSS) annually (12-, 24-, and 36-month visits) post randomization. PROs/Quality of life questionnaires should be collected prior to any procedures on these specified visits.

- Two (2) systematic biopsies (Biopsy 1 & Biopsy 2; ≥ 10 cores each) will be administered as standard of care. Additional cores may be collected by MRI guidance per Investigator discretion; however, MRI targeted cores collected at baseline should be repeated for Biopsy 1 & Biopsy 2 (Appendix 7 of the protocol).

Biopsy 1 will be administered between 12 and 18 months, and Biopsy 2 will be administered between 33 and 39 months post randomization. All H&E and special stained slides will be assessed for histopathologic grading by BICR. Slides from each biopsy will be considered as a group to determine the ISUP Grade Group as opposed to any single slide. The BICR is blinded to a subject's study arm randomization. BICR will receive the local pathology staining methods and Gleason score. All subject information should be redacted from the local pathology reports and slides. Local pathology reports and slides will be identified only by study subject number. All slides will be returned to the clinical trial site.

Post randomization, central pathology requested formalin-fixed paraffin-embedded (FFPE) tissue blocks, identified by study subject number, will be sent to the central pathology lab for cutting and slide preparation for immunohistochemistry (IHC) and genomic analysis. All tissue blocks will be returned to the clinical trial site.

Upon study completion, if the primary hypothesis is met ([Section 12.6.1](#)), subjects on the control arm may be offered sipuleucel-T.

[figure not shown]
Follow-up Phase:

Once a subject from either the sipuleucel-T or control arms completes the end of Active Phase visit, they will enter the Follow-up Phase and complete Follow-up Phase visits every 6 months starting from their last Active Phase visit. The Follow-up Phase visits end when the last subject enrolled completes Biopsy 2 and the end of Active Phase visit or until the study is terminated by the sponsor. All subjects will be assessed for:

- Survival status
- PROs/Quality of life questionnaires
- PSA levels (as available by local laboratory)
- Prostate cancer disease progression
- All anti-prostate cancer therapies
- All AEs and SAEs

Figure 1

Figure 1: Study Schematic

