12.7 Safety Analyses

12.7.1 Adverse Events

A summary of AEs, including the number and percentage of events reported, and the number and percentage of subjects

- reporting at least one AE,
- with at least one grade ≥ 3 AE,
- with at least one SAE,
- with at least one study drug related AE (probable or possibly related),
- with an AE leading to death

will be presented by study treatment arm in the Safety population. In the summary by worst National Cancer Institute Common Terminology Criteria for Adverse Events (NCI CTCAE) v5.0 grade, the AE with the highest or most severe grade will be counted when subjects have multiple AEs in a SOC or PT.

A breakdown of the number and percentage of subjects reporting each kind of AE above, categorized by SOC and PT, will be also presented. This breakdown will be sorted by PT within SOC. Note that counting will be by subject and not by event and subjects are only counted once within each SOC or PT. This breakdown will be repeated and sorted by descending frequency of PTs in the sipuleucel-T arm for subjects reporting at least one AE and subjects reporting at least one grade ≥ 3 AE. This breakdown will also be

repeated by worst CTCAE grade for subjects reporting at least one AE and subjects reporting at least one grade ≥ 3 AE, sorted by PT within SOC.

AEs occurred within 1 day after any leukapheresis will be summarized. Similarly, AEs occurred within 1 day after any infusion will be summarized.

Listings of AEs will also be presented.

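### The by-arm AE and SAE tables run to the last study visit without separating events after later prostate cancer therapy, and no between-arm table covers the treatment period

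*SAP*

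**What the plan says.** Collection is broad. Protocol 9.1.4 states: "All AEs and SAEs in the sipuleucel-T arm and control arm will be collected from randomization", and it continues to each man's last study visit. SAP 8.4.1 repeats this, then says "For this study, treatment emergent adverse event (TEAE) is not defined" and sets the reporting rule: "All adverse events occurring after the first leukapheresis (after randomization for the control arm) will be summarized".

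SAP 12.7.1 tabulates from that set, by arm: any AE, grade 3 or higher AEs, SAEs, drug-related AEs and fatal AEs, with breakdowns by SOC and preferred term, worst-grade tables and listings. Two tables have a time window. One is described as "AEs occurred within 1 day after any leukapheresis will be summarized", and the other does the same for infusions.

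Under Protocol 6.8, prostatectomy, radiation or ADT does not end participation: "subjects who receive any of the following will go from Active Phase of the study to the Follow-up Phase of the study". The Follow-up Phase list in SAP 6.1 still includes "All AEs and SAEs". The SAE definition in Protocol 9.2.1 includes "subject hospitalization or prolongation of an existing hospitalization" and states no exception for planned admissions. SAP 12.7.5 stops data only at withdrawal from the study.

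**The concern.** Sipuleucel-T is given over about a month, but the tables cover roughly three years or more. In that time some men will be treated for their cancer. The plan expects that to differ by arm: upgrading is designed at 0.30 against 0.16, and differential receipt of surgery, radiation and ADT is a secondary objective. Events caused by those therapies enter the safety tables through the efficacy pathway.

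The narrower tables do not isolate product toxicity between arms. The 1-day tables have no control counterpart. Relatedness is an investigator's judgement in an open-label trial. Protocol 6.7 defines a treatment-related period (to 30 days after the last infusion) for restricted therapies, but no AE table uses it.

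At stake is whether the headline percentages can be read as the safety of the product in men on surveillance.

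**Working it through.** **Design figures (Protocol 10.1, SAP 6.2).** The odds ratio is (0.84/0.16) / (0.70/0.30) = 5.25 / 2.333 = 2.25, as stated. For 300 against 150 men at one-sided 0.025, an unstratified Fisher exact test has 90.25% power, which agrees with the stated 90%. The documents give no AE, SAE or subsequent-treatment rate to reproduce.

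**How much of the summarized time is treatment time.** On the planned schedule, infusions fall near days 3, 17 and 31 after first leukapheresis. Adding 30 days gives 31 + 30 = 61 days. Biopsy 2 at 33 to 39 months is day 1004 to 1187. With first leukapheresis at day 0 to 60, the summarized time up to Biopsy 2 is 944 (1004 - 60) to 1187 days. The share is 61/944 = 6.5% down to 61/1187 = 5.1%. About 94% to 95% of the time lies outside the treatment period, before any Follow-up Phase time is added.

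**Size of the later-therapy component.** Let f be the share of upgraded men who start surgery, radiation or ADT while on study, and q the share of those with a countable event from it. Both are assumptions, taken as equal in the two arms; treatment without an upgrade is ignored.

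Gap = (0.30 - 0.16) x f x q = 0.14 x f x q

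| f | q | Control (%) | Sipuleucel-T (%) | Gap (points) |
|---|---|---|---|---|
| 0.25 | 0.10 | 0.75 | 0.40 | 0.35 |
| 0.50 | 0.25 | 3.75 | 2.00 | 1.75 |
| 0.75 | 0.25 | 5.62 | 3.00 | 2.62 |
| 0.75 | 0.50 | 11.25 | 6.00 | 5.25 |
| 1 | 0.50 | 15.0 | 8.0 | 7.0 |
| 1 | 1 | 30.0 | 16.0 | 14.0 (ceiling) |

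**Effect on a real excess.** Assume a 10% background risk and a true 3-point product excess. The table would show:

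- f = 0.50, q = 0.25: [1 - 0.87 x 0.98] - [1 - 0.90 x 0.9625] = 14.7% - 13.4% = +1.4 points
- f = 0.75, q = 0.25: [1 - 0.87 x 0.97] - [1 - 0.90 x 0.94375] = 15.6% - 15.1% = +0.55 points
- f = 0.75, q = 0.50: [1 - 0.87 x 0.94] - [1 - 0.90 x 0.8875] = 18.2% - 20.1% = -1.9 points

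(Differences are taken before rounding.)

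**The opposing component.** Up to about month 6 the sipuleucel-T schedule has about 10 AE-collecting contacts (3 leukaphereses, 3 infusions, weeks 6, 10, 14 and 26). The control schedule has 2 (months 3 and 6). More contacts tend to yield more recorded AEs. The documents give no basis for sizing this.

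**Where an early window can end.** Week 26 is counted from first infusion. First leukapheresis may be as late as day 60 and infusion follows about 3 days later, so week 26 can fall near day 63 + 182 = 245 (252 with the 7-day visit window). A split at month 6 would leave that extra contact in the later period. Biopsy 1 opens at month 12, so a window closing between these dates holds all the extra contacts on the planned schedule and precedes any upgrade found at a scheduled biopsy.

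**The case against.** The strongest reply is that nothing inferential is affected and much of the detail can already be seen. Protocol 3.2 asks for an evaluation of sipuleucel-T's safety and words only the other two secondary objectives comparatively. Protocol 10.5.2 makes the safety summaries descriptive. The SOC and preferred-term tables will often separate surgical complications from infusion or leukapheresis reactions, and SAP 12.6.2.1 reports subsequent therapy by type, reason and timing. Under a treatment-policy view, fewer complications because less surgery was needed is a genuine consequence of assignment.

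Most of this stands. It limits the point to the top-line rows and is a good reason to keep the full-period tables. It does not supply the missing comparison: an event term that either the product or a later therapy could cause cannot be apportioned from a preferred-term table, and matching listings to therapy dates by hand is not a planned analysis.

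Three stronger readings are tempting, and the documents do not support them.

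- A reader might infer that the tables have no end. They end at the last study visit; what is missing is an end or split tied to treatment or to later therapy.
- A reader might infer that an effective product would necessarily look safer. The contact imbalance works against that, and the net direction cannot be determined.
- A reader might count every prostatectomy admission as an SAE (q = 1). With an assumed 30% to 70% of upgraded men having surgery, that gives 0.14 x 0.3 to 0.14 x 0.7 = 4.2 to 9.8 points, and would offset a 5-point excess at 0.05/0.14 = 36% having surgery. But counting a planned admission is inferred only from the absence of an exclusion, and the AE definition requires an untoward occurrence. Protocol 8.11 lets upgraded men stay on surveillance, and men upgraded at Biopsy 2 may have little on-study time left for surgery.

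**Conclusion.** The point holds in limited form. The top-line by-arm AE, grade 3 or higher and SAE rows mix product toxicity with events from later cancer therapy whose receipt is expected to differ by arm. No planned table compares the arms over the treatment period. The SOC and preferred-term tables and the listings mitigate this only partly.

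The later-therapy component is 0.14 x f x q at the design rates: under 2 points when f is 0.50 and q is 0.25 or less, and 5 to 7 points only if most upgraded men are treated and half of those have a countable event. These figures rest on assumed f and q and on the design upgrade rates being realized. No error rate or decision rule depends on these tables. What is affected is whether the headline percentages can be interpreted.

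**What to change.** Keep the full-period tables and add to SAP 12.7.1, with matching definitions in 8.4.1:

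- **(a) Early window.** By-arm tables of any AE, grade 3 or higher AEs and SAEs over one fixed window counted from randomization in both arms. It should include the week-26 post-infusion visit (up to about day 245) and end before month 12; day 270 would serve. Sipuleucel-T events between randomization and first leukapheresis are already collected and should be counted here. The table will still carry the contact imbalance, which a footnote should state.
- **(b) Split at subsequent therapy.** By-arm tables of AEs starting before, and separately on or after, first subsequent prostate cancer therapy, with subject-years. Label these supportive: time to therapy may differ by arm, so the split is selective and cannot replace (a).
- **(c) Planned admissions.** A flag for planned admissions for prostate cancer treatment, so that SAEs can be shown with and without them.

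Also state how partial AE dates are placed for (a) and (b), since the start-date imputation in SAP 12.7.5 uses a first dose date that control men do not have.

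The cost is SAP wording and more output. Items (a) and (b) use AE dates and therapy start dates already collected. Item (c) may need a review of SAE reports, because the documents show no dedicated field for it.

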After Screening assessments are completed, eligible subjects will be randomized 2:1 to the sipuleucel-T arm or the control arm. Subjects randomized to sipuleucel-T arm will undergo their first leukapheresis within 60 days of randomization and will receive 3 infusions of sipuleucel-T at approximately 2-week intervals. Subjects randomized to the control arm will be followed on AS as described in the schedule of events ([Table 2](#)).

P17-1 (ProVent) Protocol

Subjects randomized to the sipuleucel-T arm will be evaluated at 0, 2, 4, 6, 10, 14, and 26 weeks following the first infusion for:

- Immune responses (Week 0 prior to first infusion is baseline)
- All anti-prostate cancer therapies
- Concomitant medications
- Adverse events (AEs) and serious adverse events (SAEs) (per reporting requirements for the sipuleucel-T arm) ([Section 9](#))

Subjects randomized to the control arm will be evaluated (office visit or phone) at 3 months following randomization for:

- Survival status
- All anti-prostate cancer therapies
- Concomitant medications
- All AEs and SAEs

Subsequently, all subjects in the sipuleucel-T and control arms will be followed every 6 months from date of randomization for at least 36 months for:

- Immune responses (sipuleucel-T arm only)
- Survival status
- PSA levels (should be collected prior to DRE and biopsy procedures)
- DRE assessments
- Prostate cancer disease progression
- All anti-prostate cancer therapies
- Concomitant medications
- All AEs and SAEs

Note, for subjects randomized to the sipuleucel-T arm, scheduled events for the 26-week visit post first infusion and first 6-month visit post randomization may take place on the same visit and only one set of immune samples need to be collected.

During the Active Phase, all subjects in the sipuleucel-T and control arms will complete:

- PROs/Quality of life questionnaires (Max-PC, SF-12, EPIC-CP, and IPSS) annually (12-, 24-, and 36-month visits) post randomization. PROs/Quality of life questionnaires should be collected prior to any procedures on these specified visits.
- Two (2) systematic biopsies (Biopsy 1 & Biopsy 2; ≥ 10 cores each) will be administered as standard of care. Additional cores may be collected by MRI guidance per investigator discretion; however, MRI targeted cores collected at baseline should be repeated for Biopsy 1 & Biopsy 2 ([Appendix 7](#)).

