(H&E) and special-stained slides from this biopsy will be submitted for BICR determination of their ISUP Grade Group classification prior to study withdrawal. All AEs considered by the investigator to be related to sipuleucel-T that are ongoing at the time of discontinuation will be followed by the investigator until resolution, return to baseline, or a determination by the investigator that no further improvement is expected. The investigator should make every reasonable attempt to ensure that the subject is contacted (via telephone or during the Early Withdrawal Visit) to obtain the final status of any AEs and concomitant medications.

After Screening assessments are completed, eligible subjects will be randomized 2:1 to the sipuleucel-T arm or the control arm, respectively. Subjects randomized to sipuleucel-T arm will undergo their first leukapheresis within 60 days of randomization and will receive 3 infusions of sipuleucel-T at approximately 2-week intervals. Subjects randomized to the control arm will be followed on AS as described in the schedule of events (Table 2 of the protocol).

Subjects randomized to the sipuleucel-T arm will be evaluated at 0, 2, 4, 6, 10, 14, and 26 weeks following the first infusion for:

- Immune responses (Week 0 prior to first infusion is baseline)
- All anti-prostate cancer therapies
- Concomitant medications
- AEs and serious adverse events (SAEs) (per reporting requirements for the sipuleucel-T arm)

Subjects randomized to the control arm will be evaluated (office visit or phone) at 3 months following randomization for:

- Survival status
- All anti-prostate cancer therapies
- Concomitant medications
- All AEs and SAEs

Subsequently, all subjects in the sipuleucel-T and control arms will be followed every 6 months from date of randomization for at least 36 months for:

- Immune responses (sipuleucel-T arm only)
- Survival status
- PSA levels (should be collected prior to DRE and biopsy procedures)
- DRE assessments
- Prostate cancer disease progression
- All anti-prostate cancer therapies
- Concomitant medications
- All AEs and SAEs

Note, for subjects randomized to the sipuleucel-T arm, scheduled events for the 26-week visit post first infusion and first 6-month visit post-randomization may take place on the same visit and only one set of immune samples need to be collected.

During the Active Phase, all subjects in the sipuleucel-T and control arms will complete:

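### AE and SAE summary tables start at randomization for control but only after first leukapheresis for sipuleucel-T, leaving up to 60 days out of one arm's tables

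*SAP*

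**What the plan says.** **Collection.** Protocol 9.1.4 states: "All AEs and SAEs in the sipuleucel-T arm and control arm will be collected from randomization". SAP 8.4.1 repeats it: "All AEs (and SAEs) in the sipuleucel-T arm and control arm will be collected from randomization". Both run to the last study visit.

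**Summary.** The same SAP section then narrows what is tabulated: "All adverse events occurring after the first leukapheresis (after randomization for the control arm) will be summarized". It offers no treatment-emergent convention as the reason: "For this study, treatment emergent adverse event (TEAE) is not defined".

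**Time between the two starting points.** Protocol 5.1: "Subjects randomized to sipuleucel-T arm will undergo their first leukapheresis within 60 days of randomization". SAP 6.1 gives the same limit.

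**Elsewhere.** SAP 12.7.1 describes the AE tables by arm and plans AE listings, with no start date for either. SAP 12.7.2 refers SAEs back to 12.7.1 and reports all-cause deaths for all randomized subjects. Protocol 10.5.5.1 lists the AE tables and has no leukapheresis restriction.

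**Safety set.** SAP 9.3 counts every control subject, but a sipuleucel-T subject only if at least part of infusion 1 was given; replaced subjects are excluded. Protocol 10.2 asks only that sipuleucel-T subjects have entered the treatment process.

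**The concern.** The secondary safety endpoint is AE incidence in each study arm, so the tables will be read side by side. Randomization is the one time origin the arms share, because control has no treatment start. The SAP uses it for study day and for baseline (SAP 8.0, 8.4.3, 8.4.4). The sipuleucel-T AE start is the exception.

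Under this rule the same event, on the same day after randomization, is counted for a control man and left out for a sipuleucel-T man not yet leukapheresed. Columns headed by arm would cover different periods at risk, and nothing in the planned tables would tell the reader so.

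**Working it through.** The plan gives no figure to reproduce here. The check is the length of the gap, then its possible effect on the percentage with any AE.

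**Step 1: the gap in each arm.** Gap = start of summary minus start of collection.

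- Control: randomization minus randomization = 0 days.
- Sipuleucel-T: first leukapheresis minus randomization = up to 60 days (Protocol 5.1, SAP 6.1).

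**Step 2: share of follow-up.** Taking 36 months as 36 × 30.4375 = 1,095.75 days:

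- 60 / 1,095.75 = 5.5% of 36 months
- 60 / 180 = 33% of the first 180 days

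These are maxima. The actual delay is not in the documents. AE collection continues into the Follow-up Phase, so the share is below 5.5% for men followed beyond 36 months.

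**Step 3: direction.** Removing events from one arm cannot raise its number of men with any AE, a grade 3 or higher AE or an SAE, nor any man's worst grade. This rule by itself can therefore only lower sipuleucel-T counts or leave them unchanged.

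**Step 4: possible size.** Assume the same constant AE rate *r* per person-year in both arms, with independent recurrences, a period *T* from randomization and a delay *L*, in years. Then

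- control: 1 − exp(−*rT*)
- sipuleucel-T as tabulated: 1 − exp(−*r*(*T* − *L*))
- understatement = the difference.

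The rates and delays are assumptions, since the documents give neither; 60 days is the permitted maximum.

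| Rate *r* | Period | Control | Sipuleucel-T, *L* = 15 / 30 / 60 days | Understatement (points) |
|---|---|---|---|---|
| 0.1 | 1,096 days | 25.9% | 25.6 / 25.3 / 24.7% | 0.3 / 0.6 / 1.2 |
| 0.5 | 1,096 days | 77.7% | 77.2 / 76.8 / 75.8% | 0.5 / 0.9 / 1.9 |
| 0.1 | 180 days | 4.8% | 4.4 / 4.0 / 3.2% | 0.4 / 0.8 / 1.6 |
| 0.5 | 180 days | 21.8% | 20.2 / 18.6 / 15.1% | 1.6 / 3.3 / 6.7 |

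(Differences were taken before rounding.) At a rate of 1.0, nearly everyone has an AE by 36 months, so the understatement there is only 0.2 to 0.9 points; over 180 days it is 2.6 to 10.9. The SAP plans no 180-day table; those rows show the effect on an early look.

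**Step 5: the safety set.** SAP 9.3 and Protocol 10.2 differ for a sipuleucel-T man who has leukapheresis but no infusion. If leukapheresis counts as entering the treatment process, the protocol includes him and the SAP leaves him out with all his AEs. No control man can be excluded in this way. SAP 12.6.1.3 records three replaced sipuleucel-T subjects and does not say whether any had leukapheresis. Moving the AE start date alone would not bring such men back.

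**The case against.** The best defence is that events before leukapheresis precede any study procedure specific to sipuleucel-T, so leaving them out gives a cleaner picture of the treatment's harm. The protocol's tie between the sipuleucel-T safety population and entry into the treatment process points the same way. That is a reasonable basis for a within-arm table. It does not justify a comparison in which control keeps the corresponding period, and Protocol 10.2 defines a population, not a time window.

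Several limits do stand. Safety is summarized descriptively, so no hypothesis test is affected. Most tables count a man once per term or organ class, so the 36-month effect is small.

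A reader might also infer more than the documents support:

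- *That the events are lost.* They are collected, SAEs go to the sponsor within 24 hours, listings have no stated start, and deaths cover all randomized men. The omission is confined to the AE and SAE summary tables.
- *That harm from central lines placed before leukapheresis is hidden.* SAP 8.2 says only "CVC use is defined as occurrence captured on the Central Venous Catheter Summary Form at any visit". No section says when lines are placed.
- *That a definite number of events is removed.* The ceiling is 300 × 60 / 365.25 = 49 person-years, if all 300 planned men waited the full 60 days. Turning that into an event count needs a rate and a delay that the documents do not give.
- *That the AE comparison as a whole favours sipuleucel-T.* That arm has much denser early contact (leukaphereses, infusions and visits to week 26) than control, which has one 3-month contact, possibly by phone. More contact may raise reporting, so the net direction is not established.

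**Conclusion.** The concern holds for the AE and SAE summary tables. SAP 8.4.1 starts them at different points in the two arms although collection starts at the same point, and no other section restores a common start. The gap is 0 days for control and up to 60 days per sipuleucel-T man, at most 5.5% of 36 months.

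If true rates are equal and lie between 0.1 and 0.5 AEs per person-year, with delays of 15 to 60 days, the sipuleucel-T any-AE percentage is understated by about 0.3 to 1.9 points over 36 months and 0.4 to 6.7 points over the first 180 days. The textual asymmetry is certain; these sizes rest on the assumed rates and delays. The effect is modest over the whole study and larger for an early comparison. It should be corrected because it is one-sided and easily avoided, not because it threatens the trial's conclusions.

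**What to change.** 1. In SAP 8.4.1 and 12.7.1, start the main by-arm AE and SAE tables at randomization in both arms.
2. Keep the post-leukapheresis summary as an additional table for the sipuleucel-T arm, labelled as within-arm.
3. Reconcile SAP 9.3 with Protocol 10.2, including the SAP sentence on replaced subjects, so that sipuleucel-T men who had leukapheresis but no infusion are not left out of these tables. State what counts as entering the treatment process. Men who never reach that point would still be outside the sipuleucel-T column, so a footnote should give their number.

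The cost is SAP wording and revised table shells; Protocol 9.1.4 already requires collection from randomization. The one small drawback is that the main sipuleucel-T tables will include some events from before any leukapheresis or infusion. The additional table in item 2 separates them.
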